13.1.2 Time to improvement of oxygenation

Oxygen saturation will be measured daily via pulse oximetry.

Time to improvement of oxygenation (in days) is defined as oxygen saturation (pulse oximetry) $>93\%$ and increased by $\geq 1\%$ from Baseline breathing only room air in the 48 hours preceding the measurement.

The time to improvement will be analyzed using a Cox proportional hazards model to estimate the hazard ratio and corresponding 95% CI for SIR1-365 dose vs placebo.

The proportional hazard regression model will include a single term for treatment. Patients without a pulse oximetry $>93\%$ with an increase $\geq 1\%$ from Baseline will be censored at the date of their last pulse oximetry measurement (meeting the preceding 48 hours room air only requirement) or the last date that supplemental oxygen was received, whichever come later.

- Patients without a post-baseline oximetry measurement who did not receive supplemental oxygen will be censored at day 1.
- Death prior to an improvement will be handled as a competing risk event.

The hazard ratio estimation of the event of interest (improvement of oxygenation) will be derived from a cumulative incidence function.

Kaplan Meier curves of time to improvement of oxygenation will be plotted for each treatment group on the same graph.

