#### 4. Objectives and Outcome Measures

Objectives	Outcome Measures
Primary	
Primary Objective: To assess the overall safety and tolerability of SIR1-365 in patients with severe COVID-19	Primary Safety Measure 
 
Proportion (%) of patients with any TEAEs during the treatment period (Baseline to Day 14)
 
 Secondary Safety Measures 
 
Proportion (%) of patients with any AEs, SAEs and drug-related AEs during the study (Baseline to Day 14 and Day 28)
 
Proportion (%) of patients with clinically significant abnormality in clinical laboratory tests and ECG during the study (Baseline to Day 14 and Day 28)
 
[REDACTED]
 
[REDACTED]
 
 
Changes in safety outcomes in patient populations with different Baseline levels of inflammatory biomarkers to assess the correlation of biomarker profile to safety outcomes.

Secondary	
1. To assess the clinical efficacy of SIR1-365 in patients with severe COVID-19	Clinical Efficacy Endpoints 
 
Change from Baseline to Day 7 and Day 14 in PaO2/FiO2 ratio
 
Time to improvement of oxygenation defined as oxygen saturation (pulse oximetry) >93% and increased by ≥1% from Baseline breathing only room air in the 48 hours preceding the measurement during the study (Baseline to Day 28)
 
Number of days without oxygen use during the study (Baseline to Day 28)
 

Objectives	Outcome Measures
	
 
Change from Baseline to Days 7, 14 and 28 in the score of the WHO ordinal scale
 
Proportion (%) of patients with clinical improvement defined as a reduction of 2 points in the WHO ordinal scale during the study (Baseline to Day 28).
 
Number of days hospitalized during the study (Baseline to Day 28)
 
Proportion (%) of patients free of respiratory failure during the study (Baseline to Day 28)
 
All-cause mortality rate during the study (Baseline to Day 28)
 
 
Changes in clinical efficacy endpoints in patient populations with different Baseline levels of inflammatory biomarkers to assess the correlation of biomarker profile to clinical efficacy outcomes

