### 5.1. Inclusion Criteria

*Patients can be enrolled into this study if all of the following criteria are met at screening visit:*

1. Hospitalized patient with clinical diagnosis of SARS-CoV-2 virus infection per World Health Organization criteria including positive nucleic acid test of any specimen (e.g., respiratory, blood, or other bodily fluid) within 2 weeks prior to screening.
2. Symptoms suggestive of severe systemic illness with COVID-19, which could include any of the following symptoms: fever, cough, sore throat, malaise, headache, muscle pain, gastrointestinal symptoms, or shortness of breath at rest, or respiratory distress.
3. Clinical signs indicative of severe systemic illness with COVID-19, which could include any of the following clinical signs: respiratory rate  $\geq 30$  per minutes, heart rate  $\geq 125$  per minute,  $\text{SpO}_2 \leq 93\%$  on room air,  $\text{PaO}_2/\text{FiO}_2$  ratio  $< 300$  mmHg, or lung infiltration  $>50\%$  on chest X-ray imaging.
4. Patients with plasma CRP level  $>50$  mg/L or 4x upper limit of normal range at screening.
5. Men or women  $\geq 18$  but  $\leq 80$  years of age at the time of signing the informed consent form.
6. Use of home oxygen is allowed
7. Patient is able to understand the purpose and risks of the study and provide signed and dated informed consent or have a legal representative provide consent and authorization to use protected health information (in accordance with national and local patient privacy regulations).
8. Patient is able to swallow tablets or receive delivery of oral suspension via a nasogastric tube.
9. Patient agrees not to participate in another interventional study after signing the informed consent form and until the end of study (EoS) visit has been completed.

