### **8.1. Clinical Efficacy Assessments**

Clinical efficacy of SIR1-365 in hospitalized patients with severe COVID-19 will be assessed by monitoring the changes from baseline on the following parameters between the treatment groups. All the assessment will be performed and administered per the SoA. The results will be documented in the eCRF.

For eligible and enrolled patients, the values of their last efficacy assessments obtained on Day 1 before dose will be used as baseline value.

Correlation of biomarker profile to efficacy outcomes will be determined by analyzing the changes on efficacy outcomes in patient populations with different baseline levels of biomarkers. Details of this analysis will be included in the Statistical Analysis Plan (SAP).

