8.2 Standard Calculations

Variables requiring calculations will be derived using the following formulas:

- Baseline: A Baseline value, unless specified otherwise, is the last non-missing value recorded prior to the first dose of study drug.
- Study day: For a given date, study day will be calculated as the number of days from the day of first dosing of study drug, labeled day 1, therefore:

Study day = date of event/measurement - date of first dose of study drug + 1, for events/measurements on or after first dose

Study day = date of event/measurement - date of first dose of study drug, for events/measurements before first dose

- Durations (days): Durations, expressed in days, will be calculated as follows:

Duration in days = (Stop date/time of event – Start date/time of event)/(3660x24)

If the stop or start time is missing, only the date information will be used as follows:

Duration in days = Stop date of event – Start date of event + 1

- Height: Height entries made in inches are converted to centimeters using the following formula:

Height (cm) = Height (in) × 2.54

- Weight: Weight entries made in pounds are converted to kilograms using the following formula:

Weight (kg) = Weight (lb)/2.2046

- Body Mass Index (BMI): BMI is calculated using height and weight and is calculated using the following formula:

BMI (kg/m²) = Weight (kg) / [[Height (cm) / 100]²]

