12.1 Clinical Efficacy Variables

Clinical Efficacy Endpoints:

- Change from Baseline to Day 7 and Day 14 in PaO₂/FiO₂ ratio
- Time to improvement of oxygenation defined as oxygen saturation (pulse oximetry) >93% and increased by $\geq 1\%$ from Baseline breathing only room air in the 48 hours preceding the measurement during the study (Baseline to Day 28)
- Number of days without oxygen use during the study (Baseline to Day 28)

- Change from Baseline to Days 7, 14, and 28 in the score of the WHO ordinal scale
- Proportion (%) of patients with clinical improvement defined as a reduction of 2 points in the WHO ordinal scale during the study (Baseline to Day 28)
- Number of days hospitalized during the study (Baseline to Day 28)
- Proportion (%) of patients free of respiratory failure during the study (Baseline to Day 28)
- All-cause mortality rate during the study (Baseline to Day 28)

Inflammatory Biomarker Measures:

- Change from Baseline to Day 7 and Day 14 in plasma CRP levels
- Time and number of the patients to reach 50% reduction from Baseline in plasma CRP level during the treatment period (Baseline to Day 14)
- Change from Baseline to Day 7 and Day 14 in inflammatory biomarker levels including ferritin, lymphocytes, and neutrophil to lymphocyte ratio
- Change from Baseline to Day 7 and Day 14 in serum cytokine levels including IL-6, TNF- α , IL-1 β , IL-7, IL-8, IL-9, IL-10, total IL-18, G-CSF, and GM-CSF
- Change from Baseline to Day 7 and Day 14 in serum chemokine levels including CXCL-1, CXCL-9, CXCL-10, IP-10, MCP-1 and MIP-1 α

Biomarker Assessment for Kidney Injury:

- Change from Baseline to Day 7 and Day 14 in urine NGAL level
- Change from Baseline to Day 7 and Day 14 in urine KIM-1 level

Biomarker Assessment for CV Endothelial Cell Damage:

- Change from Baseline to Day 7 and Day 14 in serum VWF antigen level
- Change from Baseline to Day 7 and Day 14 in serum P-selectin level
- Change from Baseline to Day 7 and Day 14 in serum soluble thrombomodulin level

Biomarker Assessment for Target Engagement:

- Change from Baseline to Day 7 and Day 14 in plasma and/or PBMC pRIP1 level
- Change from Baseline to Day 7 and Day 14 in plasma and/or PBMC pMLKL level

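### Time to improvement of oxygenation compares a room-air SpO2 with a Baseline that may have been taken on oxygen, so recovered patients with a high on-oxygen Baseline can be censored as not improved

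*SAP*

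**What the plan says.** SAP 12.1 joins two saturation conditions, "oxygen saturation (pulse oximetry) >93% and increased by" at least 1%, and SAP 13.1.2 repeats them, with the rise measured "from Baseline breathing only room air in the 48 hours preceding the measurement". Protocol section 4 words the rise as "increased by ≥1% from Baseline breathing only room air in the 48 hours preceding the measurement". In SAP 13.1.2 the censoring sentence refers to oximetry measurements "meeting the preceding 48 hours room air only requirement", which places the room-air condition on the post-baseline reading.

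Baseline carries no such condition. SAP 8.2 says that, unless otherwise specified, a Baseline value "is the last non-missing value recorded prior to the first dose of study drug". Protocol 8.1 says that for enrolled patients "the values of their last efficacy assessments obtained on Day 1 before dose will be used as baseline value". Protocol 10.3 gives the same general rule as the SAP.

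The entry criteria make on-oxygen Baselines likely. Room-air saturation of 93% or less is only one item in a list "which could include any of the following clinical signs" (protocol 5.1). The same section states "Use of home oxygen is allowed", and protocol 5.2 tolerates periodic high-flow oxygen. SAP 13.1.1.1 takes FiO2 from the saturation page of the CRF, so readings on supplemental oxygen are expected.

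Patients without the event are censored. The Cox model has treatment as its only term, and the strata (SAP 7) are age group, dexamethasone use and remdesivir use.

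**The concern.** Saturation on oxygen and saturation on room air are not on the same footing. A patient held at 98% on nasal oxygen who recovers to a stable 97% on room air has plainly improved, yet has not risen by 1% and is censored. A patient who moves from 93% to 94% on room air has the event. For patients with a high Baseline, event status then depends partly on how much oxygen was running when Baseline was read.

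At stake are the number of events and the size of the estimated hazard ratio. The trial is not powered for this endpoint, but SAP 6 says its estimates are meant to inform later studies, so an estimate pulled toward 1 has a cost.

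**Working it through.** The plan gives no event count, effect size or power for this endpoint (SAP 6), so there is no figure to reproduce. The check has five steps.

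**1. Lowest room-air reading that counts.** With whole-percent readings and Baseline b, the threshold is max(94, b + 1) if the rise is absolute and max(94, 1.01 × b rounded up) if it is relative. Both give the same result:

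| Baseline SpO2 (%) | Needed on room air (%) |
|---|---|
| 93 or less | 94 |
| 94 | 95 |
| 95 | 96 |
| 96 | 97 |
| 97 | 98 |
| 98 | 99 |
| 99 | 100 |
| 100 | 101, impossible |

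**2. Comparison with the SAP's own FiO2 arithmetic.** Take a hypothetical patient at 98% on FiO2 40% who recovers to 96% on room air (21%). With the conversion table in SAP 13.1.1.1, the derived ratio goes from 112/40 × 100 = 280 to 86/21 × 100 = 410. Section 13.1.1.1 shows clear improvement; section 13.1.2 records none. The ratio rises for any Baseline FiO2 above 112/410 × 100, about 27%. A ratio of 280 is also below the 300 mmHg entry sign in protocol 5.1, so such a patient could plausibly be enrolled.

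**3. Precision.** The standard error of the log hazard ratio is roughly proportional to 1/√(events). If a share f of events is blocked, the interval widens by √(1/(1 − f)): 1.054 at f = 10%, 1.118 at 20% and 1.195 at 30%, that is about 5, 12 and 20%. The starting event count cancels. For scale, if 70% of 60 patients (42) would have had the event, 42 × 0.9, 0.8 and 0.7 leave about 38, 34 and 29. Both f and the 70% are assumptions.

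**4. Dilution.** Blocked patients stay in the risk set until censored. A simulation assumed a true hazard ratio of 2.0 and a 60% control event rate by Day 28 among patients able to have the event. A share f of patients could never have it, all were followed for 28 days, and there were no deaths. The hazard ratio comes from one large data set per f (8,000 per arm); events and power come from 500 trials of 30 per arm.

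| f (patients) | Estimated HR | Events of 60 | Power |
|---|---|---|---|
| 0% | 2.0 | 43 | 59% |
| 20% | 1.7 | 35 | 34% |
| 30% | 1.7 | 30 | 26% |
| 50% | 1.6 | 22 | 16% |

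The SAP censors at the later of the last qualifying reading and the last oxygen date, which can fall before Day 28, so actual dilution could be smaller.

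**5. Chance imbalance.** The between-arm difference in f has standard deviation √(2f(1 − f)/30): 7.7, 10.3, 11.8 and 12.9 percentage points at f = 10, 20, 30 and 50%. Neither the strata nor the model absorbs it.

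**The case against.** The scope is limited. Any Baseline of 93% or less, on oxygen or not, is unaffected. At 94-96% the extra demand is 1-3 points, and daily oximetry in hospital gives repeated chances to meet it. The documents give neither the distribution of baseline saturation nor the share of patients on oxygen, so every magnitude rests on an assumed f. All of this stands.

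A reader might infer that the hazard ratio is biased for or against SIR1-365. The documents do not support that. Baseline precedes treatment and allocation is randomised 1:1, so the blocked share is equal between arms in expectation. What remains is lost events, dilution and chance imbalance.

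A reader might also take the definition to mean a room-air Baseline, which would leave patients on oxygen without one. The reference to the 48 hours before the measurement, and the censoring sentence, rule that out. Even on that reading, saturation is also recorded at screening, so some patients would have an earlier room-air value.

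Recovery is also captured without this ceiling by oxygen-free days, the WHO scale and PaO2/FiO2. That lowers the priority but does not repair this endpoint.

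Finally, dropping the rise only for on-oxygen Baselines makes the event rule differ by baseline oxygen status and leaves a ceiling for high room-air Baselines. The first is acceptable because the status is fixed before treatment, and 48 hours off oxygen with more than 93% is itself improvement for these patients. The second is a real gap that the fix must cover.

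**Conclusion.** The point holds within limits. The rule misclassifies some recovered patients whose Baseline was read on oxygen: it is increasingly demanding from 94%, very hard to meet at 97-99% and impossible at 100%. No other section repairs it. It does not misclassify every patient on oxygen, and it does not create a systematic difference between arms.

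The threshold table follows from the text, given whole-percent readings. The interval widening of 5, 12 and 20% assumes that 10, 20 or 30% of events are blocked; the dilution from 2.0 to about 1.6-1.7 rests on the simulation assumptions above. Priority is low to moderate, because this is one of several unpowered secondary endpoints in a study whose primary objective is safety.

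**What to change.** - In SAP 13.1.2, for patients whose Baseline saturation was on supplemental oxygen, define the event as SpO2 above 93% after 48 hours on room air only. For on-oxygen Baselines of 94-100% the threshold then becomes 94%, instead of 95% up to unattainable.
- Keep the 1% rise only where Baseline was on room air. State how room-air Baselines too high to be exceeded are handled, for example by reporting their number by arm and repeating the analysis without them.
- Keep the current definition as a sensitivity analysis.
- Record the change in SAP 15, which now reports none.
- Reconcile protocol 10.3.1, which omits the 93% threshold and so makes the rise the only saturation criterion, with protocol 8.1.2 and SAP 13.1.2.

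The cost is one derivation, one extra table and short text edits in both documents, made before unblinding. No new data are needed: FiO2 is on the saturation page (SAP 13.1.1.1), and SAP 13.1.3 already derives room-air time from the saturation and oxygen-requirement eCRFs.

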11.7.1 Time to first time back to normal

Time to first time back to normal (in days) is the number of days between the date of first study drug administration and the first date that the result of a coagulopathy parameter returns back to within a normal range.

Time to first time back to normal will be analyzed using a Cox proportional hazards model to estimate the hazard ratio and corresponding 95% CI for SIR1-365 dose vs placebo.

The proportional hazard regression model will include a single term for treatment.

- Patients with a baseline value falling within the normal range will be censored on the first date of study drug administration.
- Death prior to returning back to normal will be handled as a competing risk event.
- Patients that do not return back to normal over the assessment period will be censored at the date of last assessment
- Patients with no post-baseline assessment value will be censored at Day 1.

The hazard ratio estimation of the event of interest (first time back to normal) will be derived from a cumulative incidence function. The Kaplan Meier estimate of median time to event will also be presented for each treatment group.

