13.1.4.1 Time to clinical improvement

Time to clinical improvement is defined as the number of days between the date of first study drug administration and the first date a patient achieves a 2-point reduction on the WHO ordinal scale.

Time to clinical improvement will be analyzed using a Cox proportional hazards model to estimate the hazard ratio and corresponding 95% CI for SIR1-365 dose vs placebo.

The proportional hazard regression model will include a single term for treatment.

- Death prior to clinical improvement will be handled as a competing risk event.
- Patients that do not show any clinical improvement over the assessment period will be censored at the date of last assessment.
- Patients with no post-baseline assessment value will be censored at Day 1.

The hazard ratio estimation of the event of interest (clinical improvement) will be derived from a cumulative incidence function. The Kaplan Meier estimate of median time to event will also be presented for each treatment group.

Table 12.1.4 Categories for WHO Ordinal Scale

Patient State	Descriptor	Score
Uninfected	Uninfected; no viral RNA detected	0
Ambulatory Mild Disease	Asymptomatic; viral RNA detected	1
	Symptomatic; Independent	2
	Symptomatic; Assistance needed	3
Hospitalized: Moderate disease	Hospitalized; no oxygen therapy	4
	Hospitalized; oxygen by mask or nasal prongs	5
Hospitalized: Severe disease	Hospitalized; Oxygen by NIV or High flow	6
	Intubation & mechanical ventilation, $pO_2/FIO_2 \geq 150$ or $SpO_2/FIO_2 \geq 200$	7
	Mechanical ventilation $pO_2/FIO_2 < 150$ ($SpO_2/FIO_2 < 200$) or vasopressors	8

	Mechanical ventilation $pO_2/FIO_2 < 150$ and vasopressors, dialysis or ECMO	9
Death	Dead	10

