As a sensitivity analysis, to assess the impact of missing data, if more than 10% of patients in either arm has missing Day 7 CRP values, a MMRM analysis will be performed. The plasma CRP levels will be analyzed by a MMRM with treatment group, Day (Days 2 to 14), and treatment group-by-Day interaction as fixed factors, and the Baseline score as a continuous covariate. Day will be used as the repeated measure using an unstructured covariance structure. For both treatment groups, at Day 7, the geometric LS mean in plasma CRP levels and corresponding 95% CI will be presented. The output will also include the estimated geometric LS mean ratio for SIR1-365 dose and placebo, the corresponding 95% CI and corresponding two-sided P-value for the ratio.

Additionally, the primary analysis for plasma CRP level on Day 7 and Day 14 will be repeated for PP set with no missing data imputation.

A separate summary table will be produced, similar to what is described above, summarizing the results at Day 7 (assessments taking place on study day 7) and Day 14 (assessments taking place on study day 14). For any patients with missing Day 7 results, the Day 7 results will be imputed using the last value reported prior to study day 7. Similarly, Day 14 missing observations will be imputed with the last available assessment that took place after study day 7 and prior to study day 14. A summary table will be produced on the PP set, summarizing these (imputed and reported) results.

Time to 50% reduction:

Time (days) to 50% reduction from Baseline in plasma CRP level during the treatment period will be analyzed using a Cox proportional hazards model to estimate the hazard ratio and corresponding 95% CI for SIR1-365 dose vs placebo.

The proportional hazard regression model will include treatment as a fixed effect.

- Patients without a 50% reduction will be censored at the date of their last CRP assessment.
- Patients with no post-baseline CRP value will be censored at Day 1.
- Death, prior to 50% reduction, will be handled as a competing risk event.

The hazard ratio estimation of the event of interest will be derived from a cumulative incidence function. The number and percentage of patients to reach 50% reduction from Baseline in plasma CRP level from Baseline to Day 14 will also be summarized. This analysis will be performed in the ITT set.

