Kaplan Meier curves of time to 50% reduction from baseline in plasma CRP level will be plotted for each treatment group on the same graph.

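### Five SAP time-to-event analyses make death a competing risk but display the result by Kaplan-Meier, with no rule for how deaths enter the curves and medians

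*SAP*

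**What the plan says.** Five SAP sections carry a rule that death before the event is a competing risk, and all five take the hazard ratio from a cumulative incidence function. Each pairs this with a Kaplan-Meier display:

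- **13.1.2, improvement of oxygenation.** Rule: "Death prior to an improvement will be handled as a competing risk event". Display: "Kaplan Meier curves of time to improvement of oxygenation will be plotted for each treatment group on the same graph".
- **14.1.1, 50% reduction in CRP.** Rule: "Death, prior to 50% reduction, will be handled as a competing risk event". Display: "Kaplan Meier curves of time to 50% reduction from baseline in plasma CRP level will be plotted".
- **13.1.4.1, clinical improvement on the WHO scale.** Rule: "Death prior to clinical improvement will be handled as a competing risk event". Display: a Kaplan-Meier median per arm.
- **11.7.1, coagulopathy parameters back to normal.** Rule: "Death prior to returning back to normal will be handled as a competing risk event". Display: "The Kaplan Meier estimate of median time to event will also be presented for each treatment group".
- **14.1.2.1, ferritin, lymphocytes and neutrophils back to normal.** Same rule and same display as 11.7.1.

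The censoring rules cover patients without the event in general and do not mention deaths. For oxygenation, a non-improver is censored at the last qualifying oximetry reading "or the last date that supplemental oxygen was received, whichever come later". As far as it could be read, the figure index in SAP Appendix 5 lists the two Kaplan-Meier time-to-event figures and no cumulative incidence figure.

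Protocol 10.3.1 (oxygenation) and 10.3.3 (CRP) contain no competing-risk rule. SAP 15 records no changes to the protocol analyses.

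**The concern.** In a Kaplan-Meier estimate a patient who dies before improving must be handled in one of three ways: censored, counted as an event, or kept at risk to the end of follow-up. With no other censoring, only the last gives the share of all randomized patients who improve. The SAP does not choose.

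Censoring is the usual practice. It treats a patient who died as someone who would have gone on to improve at the same rate as the survivors. That raises the displayed share improved and can shorten the median, and it does so more in the arm with more deaths. The model and the figure in one section would then handle the same death differently.

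Oxygenation is where this matters most. It is a listed secondary endpoint, and the text of 13.1.2 plans no proportion improved, so the curve is the only absolute display described there. WHO improvement and CRP reduction already have plain proportions (SAP 13.1.4 and 14.1.1). SAP 6 says that the estimates are meant to help plan later studies, so absolute levels have some use beyond the hazard ratio.

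**Working it through.** The documents give no death rate, improvement rate or other figure on this point, so there is nothing to reproduce. The text check comes first, then an illustration of size.

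**Text check.** Sections with a competing-risk rule for death: 5. Of these, sections whose stated time-to-event display is Kaplan-Meier: 5 (2 curves, 3 medians). Sections that plan a cumulative incidence display: 0. Sections that say how deaths enter the Kaplan-Meier estimate: 0.

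**Oxygenation, assumed inputs.** One arm of n = 30 (the planned size, SAP 6), follow-up complete to Day 28, and x = 18 improvers, one each on Days 4, 5, 7, 8, 10, 11, 12, 14, 15, 17, 18, 20, 21, 22, 24, 25, 27 and 28. There are d = 3 deaths without improvement. A death on an improvement day is censored after the improvement.

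- Cumulative incidence with death competing: 18/30 = 60.0%.
- Kaplan-Meier, deaths kept at risk to Day 28: 60.0%.
- Kaplan-Meier, deaths censored, all before Day 4: 18/27 = 66.7%.
- Deaths censored on Days 5, 10, 15: 1 − (28/30)(24/27)(19/23)(9/18) = 1 − 0.343 = 65.7%.
- Deaths censored on Days 10, 20, 27: 1 − (25/30)(17/24)(11/16)(9/10) = 1 − 0.365 = 63.5%.
- Deaths censored after the last improvement: 60.0%.
- Deaths counted as events: 21/30 = 70.0%.

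**How the gap scales.** With deaths before the first improvement, the gap is x/(n − d) − x/n = x·d/[n(n − d)]. For 18 improvers and 1, 2 or 3 deaths it is 2.1, 4.3 or 6.7 points. For 3 deaths and 12 or 24 improvers it is 4.4 or 8.9 points.

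With deaths spread over follow-up (constant cause-specific hazards, true improved share p = 0.60, died share q), the censored estimate is 1 − (1 − p − q)^[p/(p + q)]. This gives 61.3%, 64.4%, 70.1% and 78.5% for 1, 3, 6 and 9 deaths in 30.

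**Contrast between arms.**
- Three early deaths in each arm, 20 v 18 improvers: 20/27 − 18/27 = 7.4 points displayed against 2/30 = 6.7 true.
- 18 of 30 improve in both arms, but only one arm has three early deaths: 66.7% v 60.0% displayed, a 6.7-point advantage for the arm with the deaths, against a true difference of zero.

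**Medians, assumed inputs.** The median is the first day on which the estimate reaches 50%.

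- WHO scale, n = 30, improvers 5, 8 and 1 at Days 7, 14 and 28, three deaths before Day 7. Kept at risk: 14/30 = 46.7%, median not reached. Censored before Day 7: 1 − (22/27)(14/22)(13/14) = 51.9%, median Day 28. Censored at Day 7: 1 − (25/30)(14/22)(13/14) = 50.8%, median Day 28.
- Laboratory normalization, 20 abnormal at baseline, 9 normalize (2, 2, 2, 2, 1 at Days 3, 7, 10, 14, 28), three deaths. True: 9/20 = 45.0%, median not reached. Deaths censored on Days 4 to 6: 1 − (18/20)(13/15)(11/13)(9/11)(8/9) = 52.0%, median Day 28. Deaths on Days 8, 9, 12: 50.1%, median Day 28. Deaths on Days 15 to 17: 46.7%, median not reached.

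For scale, the Clopper-Pearson 95% interval for 18/30 is 40.6% to 77.3%.

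**The case against.** The strongest reply is that this is one missing sentence about a display. The SAP already names death as a competing risk in each section, and a programmer could carry that rule into the curve by keeping deaths at risk, in which case the figures above show no gap. For the two listed time endpoints only a figure is affected. The three medians belong to time analyses that are not listed as endpoints. The study is exploratory and unpowered, and mortality has its own summary. All of this stands, and it sets the grade. It does not supply the missing rule, and Kaplan-Meier by default censors.

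The size can also be challenged. The 66.7% needs all three deaths before Day 4, although patients unlikely to survive 2 days are excluded. The changes from not reached to Day 28 come from inputs chosen close to 50%. Both objections are fair: the figures show direction and order of size and do not predict anything.

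A reader might take three as the most deaths possible, from the enrolment-halting rule in Protocol 7.2. The text does not support that. The rule pauses enrolment when deaths in the treatment group exceed three, pending IDMC review. It caps nothing among patients already enrolled, does not cover placebo, and allows enrolment to resume.

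Discharge is a further limit. After discharge oximetry is sparse, and the follow-up visit may be by phone with safety data only. Censoring of discharged patients affects Kaplan-Meier and Aalen-Johansen alike, so the change proposed here deals with deaths only. Finally, the contents of the oxygenation summary table (14.2.2.1) are not shown and may include event counts.

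**Conclusion.** The inconsistency is in the text: all five sections pair a competing-risk rule with a display that has no place for a competing event, and none says what happens to deaths. It is minor. If deaths are censored, the displayed share is too high by an amount that depends on the number and timing of deaths: 0 to 6.7 points in the illustration with 18 improvers and 3 deaths in 30, more with more deaths. That rests entirely on assumed counts and complete follow-up. If deaths are kept at risk, the gap is nil.

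A reader might infer that the planned results are biased, or that the treatment comparison is. The documents do not support either. The bias depends on a choice the SAP leaves open, and equal early deaths in both arms barely move the contrast. The hazard ratios already use the competing-risk rule, and the mortality summary and the primary TEAE outcome are untouched.

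Two clarifications belong with it. The hazard ratio reads most naturally as a subdistribution hazard ratio but is not named. The competing-risk rule is an addition to the protocol analyses that SAP 15 does not record.

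**What to change.** Replace the two Kaplan-Meier curves (13.1.2, 14.1.1) and the three Kaplan-Meier medians (11.7.1, 13.1.4.1, 14.1.2.1) with Aalen-Johansen cumulative incidence curves and medians read from them. Death is the competing event; other patients are censored as the SAP already states. For oxygenation, report the Day 28 cumulative incidence per arm with its 95% CI from the same estimator.

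In the same edit, state for each analysis whether the hazard ratio is subdistribution or cause-specific, and list the added competing-risk rule in SAP 15.

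The cost is SAP wording, two figures, three medians and a few table rows, using standard SAS options and no new data. Compared with a Kaplan-Meier display that censors deaths, shares may come out slightly lower and some medians may become not reached.
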